## **2. LIST OF ABBREVIATIONS**

Term	Definition / description
ABPM	Ambulatory blood pressure monitoring
ADRNa	Absolute distal sodium reabsorption rate
ADS	Analysis dataset
AE	Adverse event
AESI	Adverse events of special interest
AIx	Augmentation index
ALT	Alanine transaminase
ANCOVA	Analysis of covariance
APR	Absolute proximal fluid reabsorption rate
APRNa	Absolute proximal sodium reabsorption rate
AST	Aspartate transaminase
BHB	Beta-hydroxybutyric acid
BICMQ	BI customised MedDRA query
BMI	Body mass index
BP	Blood pressure
BRPM	Blinded report planning meeting
BSA	Body surface area
cAMP	Cyclic adenosine monophosphate
cGMP	Cyclic guanosine monophosphate
CI	Cardiac index
CLI	Lithium clearance
CNa	Sodium clearance
CO	Cardiac output
CPO	Cardiac power output
CPOI	Cardiac power output index
CS	Compound symmetry
CSII	Continuous Sub-cutaneous Insulin Infusion
CT	Concomitant therapies
CTP	Clinical Trial Protocol
CTR	Clinical Trial Report
DB	Double-blind

Term	Definition / description
DDNa	Distal sodium delivery
DKA	Diabetic ketoacidosis
DM&SM	Boehringer Ingelheim Data Management and Statistics Manual
DTA	Data transfer agreement
eCRF	Electronic case report form
eGFR	Estimated glomerular filtration rate
EoT	End of Treatment
ERPF	Effective renal plasma flow
FAS	Full analysis set
FDRNa	Fractional distal sodium reabsorption rate
FENa	Fractional sodium excretion
FELi	Fractional lithium excretion
FF	Filtration fraction
FPG	Fasting plasma glucose
FPR	Fractional proximal fluid reabsorption rate
FWER	Family-wise error rate
GFR	Glomerular filtration rate
HbA1c	Glycated haemoglobin
HRV	Heart rate variability
ICH	International Conference on Harmonisation
IPD	Important protocol deviation
ITT	Intention to treat
LOCF	Last-observation-carried-forward
MAP	Mean arterial pressure
MAR	Missing at random
MDI	Multiple daily injection
MedDRA	Medical Dictionary for Regulatory Activities
MMRM	Mixed-effect model repeated measures
NA	Not applicable
O*C	Oracle Clinical
OL	Open label
PD	Protocol deviation

---

Term	Definition / description
PG	Plasma glucose
PLi	Plasma lithium
PNa	Plasma sodium
PK	Pharmacokinetics
PPS	Per protocol set
PSTAT	Project Statistician
PT	Preferred term
PWV	Pulse wave velocity
Q1	Lower quartile
Q3	Upper quartile
RBF	Renal blood flow
REML	Restricted maximum likelihood
REP	Residual effect period
RIS	Run-in set
RMSSD	Root mean square successive index
RVR	Renal vascular resistance
SD	Standard deviation
SDNN	Standard deviation of normal-to-normal interval
SE	Standard error
SMQ	Standardised MedDRA query
SOC	System organ class
SV	Stroke volume
SVI	Stroke volume index
SVV	Stroke volume variation
T1D	Diabetes mellitus type 1
T2D	Diabetes mellitus type 2
TFC	Thoracic fluid content
ToC	Table of contents
TPR	Total peripheral resistance
TPRI	Total peripheral resistance index
TS	Treated set
TSAP	Trial statistical analysis plan

---

Term	Definition / description
ULi	Urine lithium
UNa	Urine sodium
ULN	Upper limit of normal
unGFR	Uncorrected glomerular filtration rate
UTI	Urinary tract infection
V	Urine flow rate
VI	Vagal index
WHO	World health organisation

### **3. INTRODUCTION**

As per ICH E9 (1), the purpose of this document is to provide a more technical and detailed elaboration of the principal features of the analysis described in the protocol, and to include detailed procedures for executing the statistical analysis of the primary and secondary variables and other data.

This trial statistical analysis plan (TSAP) assumes familiarity with the Clinical Trial Protocol (CTP), including Protocol Amendments. In particular, the TSAP is based on the planned analysis specification as written in CTP Section 7 “Statistical Methods and Determination of Sample Size”. Therefore, TSAP readers may consult the CTP for more background information on the study, e.g., on study objectives, study design and population, treatments, definition of measurements and variables, planning of sample size, randomization.

In July 2019 it was decided to terminate the trial early due to recruitment futility based on the inability to find patients with renal hyperfiltration. The study terminates with 31 patients randomised and treated. The basis will be CTP Version 4.0 and the analysis plan will be driven by the current known status of the study, in terms of the types of patients randomised.

Changes and additions from CTP version 4.0 are outlined in [Section 4](#).

SAS® Version 9.4 will be used for all analyses.

#### **4. CHANGES IN THE PLANNED ANALYSIS OF THE STUDY**

Below are the high level changes that have been made to both the recent versions of the protocol and to the deviation from the protocol analyses, following early trial termination in July 2019.

##### High level changes to recent versions of protocol:

The primary patient population was changed from diabetes mellitus type 1 (T1D) only to either T1D, diabetes mellitus type 2 (T2D) or obesity in CTP global amendment 3.

The primary analysis population was changed from non-responders to hyperfilterers, i.e. patients with a glomerular filtration rate (GFR)  $\geq 135$  mL/min/1.73m^2 at visit 4 instead of visit 8 in CTP global amendment 3. Consequently, a secondary analysis for the primary endpoint was planned to be performed on the non-responder subgroup. Further, in the secondary analysis of the primary endpoint on all patients in the full analysis set, the gradient of the treatment effect will be calculated based on randomization baseline GFR values that are centred around the mean baseline value instead of the originally anticipated value of 135 mL/min/1.73m^2, as with the changed population a baseline value of 135 mL/min/1.73m^2 is no longer considered a central value. In the first 31 patients randomized into the trial inulin was used to measure GFR for the primary endpoint analysis. However, as inulin will no longer be available, iohexol would have been used to measure GFR for the remaining patients to be randomized into the trial.

In CTP global amendment 3 the secondary endpoint filtration status was changed from a threshold of  $< 135$  mL/min/1.73m^2 to  $< 120$  mL/min/1.73m^2 in line with the lower baseline GFR values expected in the new primary analysis population of hyperfilterers compared to non-responders.

The further endpoints “protein intake” and “ratio of GFR to baseline” were removed and the further endpoint “24hour urea” was added in CTP global amendment 1.

The further endpoint “urine albumin / creatinine ratio” was removed and the further endpoints “glomerular pressure”, “efferent resistance”, “afferent resistance” and “ketones/BHB” were added in CTP global amendment 3.

Because the primary analysis population for the primary endpoint was changed in CTP global amendment 3, the sample size section was adapted accordingly.

##### High level changes to TSAP compared to protocol version 4.0:

The main deviation from the protocol-defined efficacy analyses will be on the analysing populations. In addition, one planned analysis for the primary endpoint will be removed and some further endpoints added. Subgroup analyses are now included for the eight renal haemodynamic parameters and for the 24-hour ambulatory blood pressure monitoring (ABPM) of systolic blood pressure (BP), diastolic BP and pulse rate.

Since no patients were randomised under the iohexol clearance method, reference will be made to inulin clearance only.

### *Primary endpoint analysis*

Analyses on subgroups of GFR hyperfilterers (n=2), GFR responder (n=2) and GFR non-responder (n=0) groups are not possible because there are too few patients per group. Therefore, it is not possible to test the null hypothesis of the study.

Subsequently, no per protocol set (PPS) will be determined, however, the important protocol deviations will still be identified prior to unblinding.

The subgroup of normofilterers (n=29) is very similar to the overall set of patients in the full analysis set (FAS) (n=31) and therefore, only the overall set of patients will be analysed.

For the overall set of patients, all pre-specified analyses will be implemented, except for the pre-specified analysis using screening GFR and the screening GFR by treatment interaction. Due to the high correlation between screening GFR and baseline (pre-randomisation) GFR, it is expected that this would lead to similar findings, compared to the analysis (with interaction) using pre-randomisation GFR as baseline.

The assumptions behind the models will be investigated by way of model diagnostics and the potential period effect by graphics. Otherwise, the analyses will be as per protocol.

### *Secondary endpoint analysis*

The secondary endpoint of proportion of patients with  $\text{GFR} < 120 \text{ mL/min/1.73m}^2$  will be analysed on the FAS only, and with an additional investigation of the GFR status ( $< 120$  vs  $\geq 120 \text{ mL/min/1.73m}^2$ ) at baseline, given that many of the patients are already  $< 120 \text{ mL/min/1.73m}^2$  at baseline.

### *Further endpoint analysis*

With regard to the further efficacy endpoints, these will be conducted according to protocol. For the planned analyses on the treated set (TS), only the full TS will be used.

Additional further endpoints for Tubular sodium handling will be added:

- Fractional sodium excretion (FENa)
- Absolute proximal fluid reabsorption rate (APR)
- Absolute proximal sodium reabsorption rate (APRNa)
- Fractional proximal fluid reabsorption rate (FPR)
- Absolute distal sodium reabsorption rate (ADRNa)
- Fractional distal sodium reabsorption rate (FDRNa)

Additional further endpoints for Cardiovascular and blood pressure parameters will be added:

- Cardiac index (CI)
- Stroke volume variation (SVV)
- Stroke volume index (SVI)
- Total peripheral resistance index (TPRI)
- Cardiac power output (CPO)
- Cardiac power output index (CPOI)
- Thoracic fluid content (TFC)

The plan for the analysis of the ABPM parameters will be outlined in the TSAP, as already indicated in the protocol. However, additional further endpoints will be created from the data collected. Since the ABPM data is collected automatically over a 24 hour period, the following endpoints will be determined for each of systolic blood pressure, diastolic blood pressure and pulse rate, and grouped accordingly:

- 24-hourly mean
- Night time mean, Day time mean
- Awake time mean, Sleep time mean
- Trough to peak ratio

### *Subgroup analysis*

There will be descriptive subgroup analyses to investigate the relationship between the 8 renal haemodynamic parameters (GFR and the 7 further efficacy endpoints) and screening GFR subgroups with categories ( $\leq 115$  vs  $>115$  mL/min/1.73m^2). The value of 115 mL/min/1.73m^2 approximately represents the median GFR at screening baseline.

Additionally, the relationship between the 24-hourly mean ABPM parameters (systolic BP, diastolic BP and pulse rate) and the two subgroups of baseline body mass index (BMI) ( $\leq$ median,  $>$ median) and baseline blood pressure (low, high) will be conducted. The specific values of low and high will be defined in the subgroup analysis [Section 7.9](#).

For each of these 11 endpoints, a small selection of the main graphical displays will be split by these subgroups, to try to identify patterns.

For the renal haemodynamic parameters only, a mixed-effect model repeated measures (MMRM) will be conducted.

## **5. ENDPOINTS**

This study comprises an open-label run-in treatment period with ramipril, followed by a double-blind (DB) treatment period. The DB treatment period further comprises: 1) two crossover periods, during which either empagliflozin or placebo is taken in addition to open-label ramipril (determined according to the randomised treatment sequence); 2) a washout period between the two crossover periods, during which only open-label ramipril is taken.

To avoid all ambiguity, the term “baseline” should not be used without further qualification. Measurements taken prior to the start of open-label ramipril treatment will be referred to as “screening baseline”. Measurements taken prior to randomisation to one of the two double-blind treatment sequences will be referred to as “randomisation baseline”.

Owing to the proposed data capture in this trial (as per CTP flowchart), a need to consider separate “period baselines” (i.e. baseline values prior to each of the two crossover periods) in all analyses is not envisaged. For select safety laboratory data, period baseline will be used where available.

### **5.1 PRIMARY ENDPOINT**

The primary endpoint is GFR under euglycaemic conditions after 4 weeks of double-blind treatment (either empagliflozin or placebo added to ramipril).

GFR is measured in units of mL/min/1.73m^2 (=mL•min•1.73m^-2). GFR will be calculated by the local laboratory using the inulin clearance method and then entered by the study site onto the electronic case report form (eCRF). The required euglycaemic conditions are those imposed by the clamp used in the trial.

Inulin method for post baseline visits: Two clearance measurements are taken in the derivation of each GFR reading, scheduled at 90 minutes and 120 minutes after the start of infusion respectively. The mean of the pair of GFR measurements at the relevant 4-week visits (visits 11 and 15) will be calculated and used as the primary endpoint value. If only one GFR measurement is available, the primary endpoint will be that single value.

All recorded GFR measurements on the eCRF will be considered eligible for derivation of the primary endpoint and will be included in the FAS analysis. However, any values measured outside of the visit window (see [Table 6.7: 2](#)) will not be used and will therefore not contribute to the primary endpoint derivation.

It will be assumed that any GFR values which are technically implausible or otherwise incorrect will be removed from the trial database during data cleaning prior to analysis.

### **5.2 SECONDARY ENDPOINTS**

#### **5.2.1 Key secondary endpoints**

Not applicable.

### **5.2.2 Secondary endpoint**

The secondary endpoint is filtration status after 4 weeks of double-blind treatment (either empagliflozin or placebo added to ramipril). Filtration status is defined as whether a patient has normal filtration status ( $\text{GFR} < 120 \text{ mL} \cdot \text{min}^{-1} \cdot 1.73 \text{ m}^{-2}$ , “yes”), or not ( $\text{GFR} \geq 120 \text{ mL} \cdot \text{min}^{-1} \cdot 1.73 \text{ m}^{-2}$ , “no”). GFR is calculated as for the primary endpoint.

No inferential analysis strategy with family-wise error rate (FWER) control is considered. Therefore, p-values for the secondary endpoint analysis can just be regarded as a descriptive measure of the degree of consistency of observed treatment differences with random variability. Likewise, confidence intervals can be regarded as a descriptive measure of the plausibility range of the effect size.

## 6. GENERAL ANALYSIS DEFINITIONS

### 6.1 TREATMENTS

There will be a maximum of eight treatment periods for patients included in this trial: screening, Ramipril run-in, ramipril post-treatment, on-treatment (crossover) period 1 (with either empagliflozin or matching placebo), treatment x wash-out period, on-treatment (crossover) period 2 (with either empagliflozin or matching placebo), treatment x post-treatment period, and post-study. The definitions of each of these treatment periods are defined in [Table 6.1: 1](#) below. (**Note:** ‘double-blind medication’ refers to either empagliflozin or placebo and ‘any study medication’ refers to either ramipril, empagliflozin or placebo.)

Table 6.1: 1 Definitions of treatment periods

Period	Start date	End date
Screening	Informed consent	Start date of open-label ramipril run in period – 1 day
Ramipril run-in	First administration of open-label Ramipril	Start date of DB on-treatment period 1 – 1 day, or, Date of last intake of open-label ramipril + x (for those patients who were not treated with DB medication)
Ramipril post treatment#	Date of last intake of open-label ramipril + x + 1	Last study contact.
On-treatment period 1 ‘Period 1’ or ‘Empa 25mg’ or ‘Placebo’	Date of first administration of first DB medication	Date of last administration of first DB medication + x
Treatment x washout ‘Empa 25mg washout’ or ‘Placebo washout’	Date of last intake of first DB medication + x + 1	Start date of second DB on-treatment period – 1 day. Date is not defined for patients who did not receive DB medication in period 2
On-treatment period 2 ‘Period 2’ or ‘Empa 25mg’ or ‘Placebo’	Date of first administration of second DB medication	Date of last administration of second DB medication + x
Treatment x post treatment ‘Empa 25mg post treatment’ or ‘Placebo post treatment’	Date of last administration of DB medication + x + 1 day	Date of last study contact + 1 day
Post study	Date of last study contact + 1 day	Date of trial database lock. Date is not defined for a patient that is lost to contact whilst still receiving study medication.

For efficacy, x=1 day, for AE x=7 days and for laboratory parameters x=3 days as defined in [Section 6.7](#).

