Measurements taken after the first intake of any study medication (ramipril, empagliflozin or placebo) will be considered on-treatment values if they have been obtained up to the end of the endpoint-specific follow-up period X, as defined in [Table 6.7: 1](#) below. Measurements taken after the last intake of study medication and after the endpoint-specific follow-up period X will be considered off-treatment values for the treatment in question.

Table 6.7: 1 Endpoint-specific follow-up period X for assignment to active treatment

Treatment phase	Endpoint(s)	Last day of assignment to treatment phase (days after study drug stop date)
Open-label ramipril run-in (for patient not subsequently randomised)	GFR	1
	HbA1c	7
	Waist circumference	7
	All other further endpoints	1
	Adverse events	7
	Safety laboratory measurements	3
Open-label ramipril run-in (for patient subsequently randomised)	GFR	0
	HbA1c	0
	Waist circumference	0
	All other further endpoints	0
	Adverse events	0
	Safety laboratory measurements	0
Double-blind treatment (both periods)	GFR	1
	HbA1c	7
	Waist circumference	7
	All other further endpoints	1
	Adverse events	7
	Safety laboratory measurements	3

Visit window definitions for each treatment phase and time point, based on the relevant anchor date to define relative days, are shown in [Table 6.7: 2](#). These visit windows will be used in all analyses and summaries of endpoints at specific time points.

Further details on the specific handling of GFR values outside these visit windows, or of insufficient washout, with regard to IPDs and PPS analysis are given in [Section 6.2](#).

Table 6.7: 2 Time windows for scheduled visits

Nominal visit number B	Treatment phase	Visit label	Anchor date	Planned days	Time window (actual days from anchor date)	
					Start	End
8	Run-in (OL Ramipril)	OL Week 4	First ramipril administration	28	15	42
11	Period 1 (Empa 25mg/Placebo)	Week 4	First period 1 medication administration	28	15	42
12	Washout	NA	Last period 1 medication intake	28	15 A	42
15	Period 2 (Placebo/Empa 25mg)	Week 4	First period 2 medication administration	28	15	42

A Note that the washout period itself commences on the (X+1)th day after visit 11 so at least (X+1) days are required for there to be any washout period at all.

B Any values from EOT visits also need to be assigned to the correct treatment phase and appropriate visit window, in addition to values from nominal visits 8, 11, 12 and 15.

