#### 7.8.1.1 Assignment of AEs to treatment

The analysis of adverse events will be based on the concept of treatment emergent adverse events. To this end, all AEs occurring on or within the respective treatment period will be considered ‘treatment-emergent’. For adverse events, the REP is defined as 7 days after the last dose of treatment (see [Table 6.7: 1](#)).

Owing to the trial design consisting of an open-label ramipril run-in period and the double-blind crossover periods, where periods are defined in [Table 6.1: 1](#), adverse events will be determined as treatment-emergent according to the following rules:

- For the AE summaries of the open-label ramipril run-in period, adverse events will be considered “on-treatment” if they lie on or within the run-in period, as defined in [Table 6.1: 1](#).
- For the AE summaries of the double-blind treatment period, adverse events will be considered “on-treatment” or ‘treatment emergent’ if they lie on or within on-treatment period 1 or on-treatment period 2, as defined in [Table 6.1: 1](#).

AEs occurring on or within the screening period will be referred to as “screening AEs”.

AEs occurring during the treatment x washout period will be assigned to “Treatment x washout”.

AEs occurring on or within the treatment x post treatment period will be assigned to “Treatment x post-treatment”.

AEs occurring on or within the post study period will be assigned to ‘Post study’.

AEs occurring on or within the ramipril post treatment period will be assigned to ‘ramipril post treatment’.

Section 15 summaries of treatment-emergent AEs in the open-label ramipril run-in period will be presented for the RIS.

Section 15 summaries of treatment-emergent AEs in the double-blind treatment period will be presented for the TS, by treatment.

Additional summaries of AEs including off-treatment study periods will be included in Appendix 16.1.9.2.

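### The AE periods in SAP Table 6.1: 1 can overlap: period 1 plus 7 days is not cut at the start of period 2, and post-treatment shares a day with post-study

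*SAP*

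**What the plan says.** **The period table (SAP Section 6.1, Table 6.1: 1).**

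- On-treatment period 1 ends at "Date of last administration of first DB medication + x". On-treatment period 2 opens at "Date of first administration of second DB medication".
- Washout opens at "Date of last intake of first DB medication + x + 1" and closes the day before the second double-blind period. For non-starters the row notes: "Date is not defined for patients who did not receive DB medication in period 2".
- For patients who go on to double-blind drug, the run-in row closes the day before period 1.
- The row for post-treatment after double-blind drug ends at "Date of last study contact + 1 day". The post-study row starts at that same date. The ramipril post-treatment row ends at last study contact, with no added day.
- The value of x is 7 days for AEs, 3 for laboratory data and 1 for efficacy.

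**The assignment rule (SAP Section 7.8.1.1).** A double-blind AE is treatment-emergent "if they lie on or within on-treatment period 1 or on-treatment period 2". For the off-treatment labels, "AEs occurring during the treatment x washout period will be assigned to" the washout label of the treatment concerned. The post-treatment and post-study labels work the same way and include both boundary days. No rule says which period wins when a day lies in two. Treatment-emergent AEs go to the Section 15 tables by treatment; summaries that include off-treatment periods go to Appendix 16.1.9.2.

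**Spacing of the periods.** Table 6.7: 2 plans Visit 12 at 28 days after the last period 1 intake, with a window of 15 to 42. Deviation G3.47 in Table 6.2: 1 flags a washout under 14 days. Footnote A to Table 6.7: 2 adds: "so at least (X+1) days are required for there to be any washout period at all".

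**The concern.** A period table for AEs should place each event once. This table does so at the planned spacing, apart from one boundary day, but its wording does not guarantee it.

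The first gap matters more. The run-in and washout rows each stop the day before the double-blind period that follows them, but the period 1 row has no such stop. Footnote A shows that the authors considered an interval too short to contain a washout, yet nothing says what then happens to the 7-day follow-up of period 1. An event in the overlap would count under both treatments in the by-treatment safety tables. With 31 patients randomised, even one duplicated event would be visible.

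The second gap is the extra day on the post-treatment row. It makes that row meet the post-study row on the same date, against the convention used in the ramipril post-treatment row.

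**Working it through.** The plan gives no figure to reproduce. The check applies the table's own date rules day by day, counting start and end dates as inside the period.

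**Part 1: period 1 against period 2**

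Let L be the day of the last period 1 dose, S the day of the first period 2 dose, and d = S − L. Days without double-blind drug number d − 1; open-label ramipril continues throughout.

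- Period 1 runs through L + x. Period 2 starts on L + d.
- Shared days run from L + d to L + x, so their number is max(0, x − d + 1). For AEs, x = 7 gives max(0, 8 − d).

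| d (calendar days) | Days without double-blind drug | Shared on-treatment days |
|---|---|---|
| 1 | 0 | 7 |
| 3 | 2 | 5 |
| 5 | 4 | 3 |
| 7 | 6 | 1 |
| 8 | 7 | 0 |
| 28 (planned) | 27 | 0 |

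Example with L = 28 and d = 3: period 1 runs to day 28 + 7 = 35 and period 2 starts on day 31, so days 31 to 35 (5 days) are in both.

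At the planned spacing, d = 28: period 1 runs to day 35, period 2 starts on day 56, and washout is days 36 to 55, which is 28 − 7 − 1 = 20 days. There is no overlap.

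Differences of 8 to 13 days are short relative to the plan but also give no overlap. So the problem range (d of 7 or less) lies well inside what G3.47 already flags.

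**Part 2: post-treatment against post-study**

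Let C be the date of last study contact. The post-treatment row runs from last double-blind dose + x + 1 to C + 1, and the post-study row starts on C + 1. They share exactly one day, C + 1, whatever x is.

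Example: with the last dose on day 84, last contact on day 98 and x = 7, post-treatment is days 92 to 99 and post-study starts on day 99.

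Two conditions apply:

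- The post-treatment row must be non-empty, which needs last contact at least x days after the last dose.
- The post-study row must be defined. The table leaves it undefined for a patient lost to contact while still on study medication.

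**Check of the repaired rules**

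- L = 28, d = 3: period 1 ends at the earlier of day 35 and day 30, so on day 30. Period 2 starts on day 31. No day is shared or left out, and the washout row is empty.
- Last dose day 84, last contact day 98: post-treatment is days 92 to 98 and post-study starts on day 99.

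**The case against.** **Remoteness.** The best defence is that neither overlap is likely to change a result. Part 1 needs fewer than 7 days without double-blind drug against 28 planned, and nothing in the SAP says that any patient came near this. Footnote A says when a washout exists; it is no evidence that such short intervals occurred. Part 2 needs an AE with onset exactly one day after last contact and reaches only off-treatment summaries. All of this stands, and it limits the point to a minor correction. It does not remove it, because the written rule still allows double assignment and gives no precedence.

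**A stronger reading that a reader might infer.** Washout is defined only for patients who start period 2, so one might conclude that AEs ending participation during washout disappear, or that the safety comparison is biased. The SAP does not support this:

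- Section 5 describes washout as lying between the two crossover periods, and Section 6.7 also bounds it by a second double-blind intake. Leaving it undefined for non-starters follows from that convention.
- No event is lost. For a non-starter, the post-treatment row opens on the day washout would have opened and carries the name of the drug last taken.
- AEs up to 7 days after the last dose are treatment-emergent in any case. Only the off-treatment summaries in Appendix 16.1.9.2 are affected.
- Patients may fail to start period 2 for reasons unrelated to AEs, and the SAP does not say how many did.

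Closing washout at the end-of-treatment (EoT) visit for non-starters would make matters worse for patients who stop during period 1. Take a last dose on day 20, that visit on day 21 and x = 7. On-treatment runs to day 27, washout would run backwards from day 28 to day 21, and post-treatment would start on day 22. Days 22 to 27, six days, would then be both on-treatment and post-treatment.

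**Conclusion.** The point holds as a minor defect of definition: the periods in Table 6.1: 1 are not mutually exclusive.

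- **Period 1 and period 2** overlap by 8 − d days for AEs when period 2 starts d = 7 calendar days or less after the last period 1 dose. This is the only part that can reach the Section 15 by-treatment tables. It should be rare, and the number of patients affected, if any, cannot be derived from the SAP.
- **Post-treatment and post-study** share one day, in off-treatment summaries only, under the two conditions given above.

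The result assumes inclusive start and end dates, as the assignment rule implies, and x = 7. The washout definition is a convention and not an error. No efficacy analysis is touched by either part of this AE point, and at the planned spacing no treatment-emergent AE table changes.

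**What to change.** In SAP Table 6.1: 1:

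1. End on-treatment period 1 at the earlier of last dose of the first double-blind medication + x and the day before the second double-blind medication starts.
2. End the post-treatment row after double-blind drug on the date of last study contact, as the ramipril post-treatment row already does.

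Leave the washout definition as it is. At most, add a footnote that washout columns contain only patients who started period 2, and that later off-treatment AEs of other patients appear under the post-treatment label of the drug last taken.

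The cost is two phrases, an optional footnote and the matching lines of period-derivation code. No new data are needed.
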